#### **5.2.7 Excluded medications and treatments**

Patients will be advised not to take additional vitamin C supplementation and check the labels of over-the-counter or homeopathic medication, prescribed or otherwise.

There may be the following drug interactions:

- High doses of vitamin C (>1000mg a day) may result in increased absorption of aluminium in medications containing aluminium and subsequent increased susceptibility to kidney stones.
- Anti-oxidants (e.g. vitamin C) may reduce the effect of some chemotherapeutic agents.
- Taking oestrogen and vitamin C may increase oestrogen levels
- Oral vitamin C may reduce the effectiveness of some antivirals such as protease inhibitors
- Vitamin C combined with niacin can reduce niacin’s effect

- 
- High doses of vitamin C (>2000mg a day) may reduce the response to warfarin.
  - Any reaction to the above medication will result in cessation of treatment and analysis as per intention to treat.
  - If patients had taken vitamin C or vitamin C-containing multivitamin in the preceding three months prior to enrolment in the trial they will be ineligible to participate due to the long half life (10 – 20 days) of vitamin C.

### 5.2.8 Concomitant therapy

Patients will be told prior to commencement of the study not to take vitamin C supplements during the course of the trial and to check labels of any multivitamin supplements.

Patients are advised to inform the researchers if they are to commence chemotherapy during their fifty days of treatment. In this rare instance, the researcher will liaise with the treating oncologist to determine that 500mg vitamin C is appropriate for their chemotherapy regime and the trial treatment will be stopped immediately if deemed unsuitable.

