	
examining them for positive signs as per the below criteria:
 
A: continuing pain, which is disproportional to any inciting event
 
B: The patient must report at least one symptom in three of the four following categories:
 
 
• Sensory- reports of hyperaesthesia and/or allodynia
 
• Vasomotor – reports of temperature asymmetry and/or skin colour changes and/or skin colour asymmetry
 
• Sudomotor/oedema – reports of oedema and/or sweating changes and/or sweating asymmetry
 
• Motor/trophic – reports of decreased range of motion and/or motor dysfunction (weakness/tremor/dystonia) and/or trophic changes (hair/nail/skin)
 
 
C: The clinician must observe at least one sig at the time of the evaluation in two or more of the following categories:
 
 
• Sensory- evidence of hyperalgesia (to pinprick) and/or allodynia and/or deep somatic pressure and/or joint movement
 
• Vasomotor – evidence of temperature asymmetry and/or skin colour changes and/or skin colour asymmetry
 
• Sudomotor/oedema – evidence of oedema and/or sweating changes and/or sweating asymmetry
 
• Motor/trophic – evidence of decreased range of motion and/or motor dysfunction (weakness/tremor/dystonia) and/or trophic changes (hair/nail/skin)
 
 
D: There is no other diagnosis that better explains the signs and symptoms
 
This outcome method has been validated(1).

To determine the demographics and characteristics of patients who develop CRPS of the lower limb
	
Patient demographics will be collected:
 
 
• Age
 
• Gender
 
• Mechanism of injury (high energy/low energy)
 
• Workers compensation injury
 
• Smoking status
 

OBJECTIVE	OUTCOME & OUTCOME MEASURE
	
 
• Diabetes
 
• Pre-existing history of CRPS
 
 
This information will be used to comment on the demographic of patients who do develop complex regional pain syndrome with the aim of predicting and preventing the condition in this patient population.

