#### 4.4.2 Exclusion criteria

Patients meeting the following criteria will be excluded from the trial:

- Current or recent (ie less than three months prior to randomization) use of vitamin C, either as an isolated substance or as part of a multi-vitamin tablet. This is because the vitamin C dosing will not be standardized if patients are also taking the vitamin, and there is potential for overdosing. Vitamin C has a half-life of 10-20 days and therefore a long exclusion period is required.
- Patients who are pregnant or breastfeeding will be excluded due to the unknown safety risks in this patient population.
- Patients who are unable to commence taking the placebo/vitamin C medication within 72 hours after their surgery will be excluded from the trial
- Patients unable or unwilling to take oral medications.
- Patients who are vegan (as the placebo acidophilus is dairy based)

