#### 4.6 Screen failures

Eligibility information will be obtained:

- Via the patient themselves – contacting the researcher/s directly
- Via the medical records, operating lists and referral screening after approval from the Human Research Ethics Committee

Patients will then have their willingness to participate recorded in the electronic medical record.

---

Those who are found, during the screening procedures, to be ineligible for trial inclusion are termed “Screen failures and they are not assigned to the intervention / are not randomised” and will be ineligible to continue in the trial.

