### 5.2.9 Discontinuation from trial intervention

Participants who discontinue trial treatment will remain in the trial. The remaining trial procedures should be completed as indicated by the trial protocol.

Participants may discontinue trial treatment for the following reasons:

- Participant / legal guardian request to discontinue trial intervention
- Investigator decision to discontinue a participant from the trial intervention if the participant:
  - Is pregnant
  - Experiences a serious or intolerable adverse event such that continued trial intervention would not be in the best interest of the participant
  - Develops, during the course of the trial, symptoms or conditions listed in the exclusion criteria
  - Requires a medication that is prohibited by the protocol
  - Requires early discontinuation for any other reason

The investigator may also withdraw all trial participants from the trial treatment if the trial is terminated.

The procedure for transitioning a participant off the trial drug and/or onto alternate therapy is as follows: patients will be advised to cease taking the medication immediately and return the unused medication to the researcher.

For the safety of all participants ceasing trial treatment, the protocol-specified safety evaluations should be undertaken to capture new safety events and to assess existing, unresolved safety events. All scheduled follow-ups of trial participants should also occur following treatment discontinuation, where possible.

In addition to the safety evaluations, the data to be collected at the time of trial intervention discontinuation will include the following:

- Reason for discontinuing medication
- Any adverse effects
- Involvement of other practitioners in treatment of adverse events

A dedicated Case Report Form (CRF) page will capture the date and the specific underlying reason for discontinuation of the trial intervention.

The participant should remain in the trial for scheduled visits for trial assessments (follow-up) per protocol.

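### The oncologist check on 500 mg vitamin C covers only chemotherapy started during dosing; the protocol's entry lists do not identify patients already receiving it

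*Protocol*

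**What the plan says.** Section 5.2.7 (Excluded medications and treatments) lists possible interactions, among them: "Anti-oxidants (e.g. vitamin C) may reduce the effect of some chemotherapeutic agents". The list is followed by a general rule: "Any reaction to the above medication will result in cessation of treatment and analysis as per intention to treat".

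Section 5.2.8 (Concomitant therapy) sets the only rule specific to chemotherapy. The trigger is: "Patients are advised to inform the researchers if they are to commence chemotherapy during their fifty days of treatment". Once it is met, "the researcher will liaise with the treating oncologist to determine that 500mg vitamin C is appropriate for their chemotherapy regime", and trial treatment stops at once if it is judged unsuitable. The section describes this as a rare event.

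Sections 4.4.1 and 4.4.2 set eligibility. The exclusion that deals with what the patient is already taking is "Current or recent (ie less than three months prior to randomization) use of vitamin C". Section 4.6 names the patient as one source of eligibility information; the other is "Via the medical records, operating lists and referral screening after approval from the Human Research Ethics Committee". Section 5.2.9, and the parallel section on treatment discontinuation, allow an investigator to stop the capsules if the participant "Requires a medication that is prohibited by the protocol", or for any other reason.

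**The concern.** The sponsor has already decided that 500 mg vitamin C alongside chemotherapy needs an oncologist's view. The rule that carries this out is tied to when chemotherapy starts, not to whether the two treatments overlap. A patient already on chemotherapy at enrolment overlaps from the first capsule, and the protocol gives no reason for treating that patient differently from one who starts in week two.

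What is at stake is the safety of an individual participant in the vitamin C arm, specifically the effectiveness of a concurrent cancer treatment. That harm would be hard to see from within the trial. A weaker response to chemotherapy is unlikely to be noticed as a reaction to a capsule, and the side-effect question in section 7.4 gives abdominal upset, back pain, nausea and vomiting as its examples.

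**Working it through.** The plan has no figure to reproduce. The check is whether any written step would identify a patient on ongoing chemotherapy or act on that fact.

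**1. Does the stated hazard apply at the trial dose?** In section 5.2.7 the aluminium entry is limited to more than 1000 mg a day and the warfarin entry to more than 2000 mg a day. The chemotherapy entry has no threshold, so 500 mg is not exempt. Section 5.2.8 confirms this by naming 500 mg as the dose the oncologist must consider.

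**2. Does the hazard depend on when chemotherapy starts?** Section 5.2.7 makes no such distinction. Only the trigger in section 5.2.8 does.

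**3. Would anything at entry identify the patient?**

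| Place in the protocol | Items | Concerning chemotherapy |
|---|---|---|
| 4.4.1 Inclusion criteria | age; consent; foot or ankle surgery at a site | 0 of 3 |
| 4.4.2 Exclusion criteria | vitamin C use; pregnancy or breastfeeding; 72-hour start; oral medication; vegan | 0 of 5 |
| 7.4 Entry questions | vitamin C use; date and time of surgery; pregnancy or breastfeeding | 0 of 3 |
| 7.4 and the section 3.2 table, baseline data | identifiers, demographics, selected history, injury and surgical details | none |

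The baseline lists contain no cancer history and no record of current medication. Records are screened under section 4.6, but against criteria that do not mention chemotherapy.

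**4. Would anything after entry identify the patient?**

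- The prompt in the section on capturing adverse events asks about new medication and changes to existing regimens. An unchanged regimen is neither.
- The reaction rule in section 5.2.7 works only after an event, and this hazard is unlikely to present as one.
- The stopping reason for prohibited medication does not clearly apply. The text under 5.2.7 expressly bars only additional vitamin C; chemotherapy appears there as a possible interaction.
- Stopping for any other reason requires the investigator to know about the chemotherapy.

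**5. How long could the exposure last?** One capsule a day for 50 days is 1 × 50 = 50 doses. No written step is certain to interrupt this for a patient whose regimen does not change, so the upper limit is all 50.

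**6. Who is exposed?** Only the vitamin C arm: about 50 of about 100 participants (sections 4.7 and 11.1). The documents give no frequency of ongoing chemotherapy in this population, and none is assumed here.

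**The case against.** The strongest reply is that no two statements conflict. Section 5.2.7 lists possible interactions, and section 5.2.8 sets a rule for one situation. The protocol nowhere says that ongoing chemotherapy is acceptable or needs no check. That stands: this is a safety rule with too narrow a trigger, not a contradiction.

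A second reply is that the patient may be found anyway. The information and consent form was not available for this review, the consent discussion covers risks, records are screened, and a question about changed medication presupposes some knowledge of the existing drugs. This stands in part. A reader might infer that nobody would discover the chemotherapy, and the documents do not support that. They support only that the protocol's own lists do not ask about it and that no criterion tells staff what to do if they learn of it.

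Third, the evidence of harm is slight. It is one hedged line with no agent, size of effect or dose, and the risk assessment in sections 2.3.1 and 2.3.3 does not mention chemotherapy. This also stands, and it limits the weight of the point. It does not remove the point, because the sponsor thought the same line enough to justify a rule for new chemotherapy.

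Rarity is a fair point too. But section 5.2.8 writes a rule for an event it calls rare, so rarity does not explain leaving out the neighbouring case.

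**Conclusion.** The concern holds as a minor safety omission. The check in section 5.2.8 does not cover chemotherapy already under way, and no listed criterion, entry question or baseline item would bring such a patient to it. Followed as written, the protocol allows up to all 50 doses without the oncologist being asked.

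Two stronger readings should be resisted. A reader might infer that participants are likely to be harmed; the documents give neither a frequency nor a size of effect, and the number affected is probably very small and may be zero. A reader might also infer that the trial's results are at risk; no feasibility outcome, CRPS analysis or sample-size statement changes.

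The conclusion assumes that the consent form and site practice, which were not available, do not already ask about current chemotherapy. If they do, the change only brings the protocol into line with them. The other interactions in section 5.2.7 are outside this point, because section 5.2.8 sets no clearance rule for them.

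**What to change.** Three linked changes:

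1. In section 5.2.8, widen the trigger to patients who *are receiving, or are to commence, chemotherapy*.
2. In section 7.4, add an entry question: *Are you currently receiving chemotherapy?*
3. For a yes answer, require the oncologist's agreement before randomisation and the first dose. Add to section 4.4.2 that the patient is ineligible if agreement is refused or cannot be obtained within the 72-hour window. The exclusion needs to be written down because section 4.4 allows randomisation only on the listed criteria.

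For patients consented before surgery, as section 7.5.1 describes, the call can be made before the operation. For those approached afterwards it must fit within the 72 hours. The existing rule for chemotherapy started during dosing stays as it is.

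The cost is one question, a few words in two sections, an occasional call to an oncologist, and a rare patient not enrolled.

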#### **5.2 Trial Intervention(s)**

Placebo and Vitamin C 500mg capsules will be sourced from Peninsula Health pharmacy and kept in a locked office in all sites. Boxes will be labelled with a randomised number only.

Pharmacy will have access to the randomised number and its allocation to placebo or vitamin C 500mg. The patient, clinicians and researchers will not be privy to the randomised group.

Other labelling of the intervention will be as applicable on the vitamin C packet. This includes:

- Expiry date
- For clinical trial use only
- Keep out of reach of children
- Store in a cool, dry place

---

Placebo and both vitamin C doses will be of similar size and taste. Patients will take one capsule orally once per day for fifty days. Capsules are stored in a cool, dry place and prepared by pharmacy.

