### 5.2.1 Description of trial investigational products

#### 5.2.1.1 Placebo

---

Active substance	Lactobacillus acidophilus and Bifidoobacterium animalis
Trade or Generic name	Blackmores Acidophilus
Dosage form	Capsule
Route of administration	Oral one capsule daily for fifty days

---

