### 6.3 Breaking of the trial blind

#### 6.3.1 On trial

The randomisation code for an individual participant may only be unblinded in emergency situations, where the Investigator decides a participant cannot be adequately treated without knowing the identity of their treatment allocation. Specifically, if the patient reports symptoms of vitamin C toxicity such as severe gastrointestinal upset or kidney stones, the randomisation code will be broken in order to communicate to the patient's treating physician(s) the vitamin C dosing. To break the randomisation code the Investigator must open the emergency unblinding envelopes provided, or contact the randomisation

---

facility/personnel. If any unblinding envelope is opened, the time, date, participant number and reason for opening must be documented.

Blinding is imperative in this trial to avoid bias and answer the specific research question and all researchers are aware of the importance of this.

It is not expected that inadvertent unblinding will occur due to strict randomisation and blinding protocols.

[figure not shown]

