## 5.2 Treatment discontinuation, participant withdrawals and losses to follow up

### 5.2.1 Discontinuation of treatment - participant remains in trial for follow up

Participants who discontinue trial treatment will remain in the trial. The remaining trial procedures should be completed as indicated by the trial protocol.

Participants may discontinue trial treatment for the following reasons:

- Participant request to discontinue trial intervention
- Investigator decision to discontinue a participant from the trial intervention if the participant:
  - Demonstrates significant non-adherence with the trial intervention
  - Experiences a serious or intolerable adverse event such that continued trial intervention would not be in the best interest of the participant
  - Develops, during the course of the trial, symptoms or conditions listed in the exclusion criteria
  - Requires a medication that is prohibited by the protocol
  - Requires early discontinuation for any other reason

The investigator may also withdraw all trial participants from the trial treatment if the trial is terminated.

The procedure for transitioning a participant off the trial drug and/or onto alternate therapy is as follows – immediate cessation of the intervention medication and opening of randomization envelope so treating clinicians are aware of the dosage.

For the safety of all participants ceasing trial treatment, the protocol-specified safety evaluations should be undertaken to capture new safety events and to assess existing, unresolved safety events. All scheduled follow-ups of trial participants should also occur following treatment discontinuation, where possible.

In addition to the safety evaluations, the data to be collected at the time of trial intervention discontinuation will include the following:

- Reason for discontinuation
- Assessment for CRPS

A dedicated Case Report Form (CRF) page will capture the date and the specific underlying reason for discontinuation of the trial intervention.

The participant should remain in the trial for scheduled visits for trial assessments (follow-up) per protocol.

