## **11 STATISTICAL METHODS**

### **11.1 Sample Size Estimation**

Sample size is not formally determined a priori, as the aim of this randomised pilot study is to determine feasibility for a future definitive randomised trial. However, we deem a sample size of at least 50 participants per arm as reasonable for allowing estimation of key feasibility parameters.

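### Section 5.2.8 clears a blinded capsule for use during chemotherapy after asking the oncologist about only one of its two possible contents

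*Protocol*

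**What the plan says.** Protocol section 5.2.8 (Concomitant therapy) asks participants to tell the researchers if they are to start chemotherapy during the 50 treatment days. In that event "the researcher will liaise with the treating oncologist to determine that 500mg vitamin C is appropriate for their chemotherapy regime". The trial treatment is stopped at once if found unsuitable. Continuation in the other case is implied rather than spelled out.

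The rest of the protocol sets the context:

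- **Blinding.** Section 5.2: "The patient, clinicians and researchers will not be privy to the randomised group".
- **Placebo contents.** The product table under 5.2.1 gives the placebo's active substance as "Lactobacillus acidophilus and Bifidoobacterium animalis".
- **Active capsule contents.** The companion table lists ascorbic acid 500mg with citrus bioflavonoids extract 50mg.
- **Named interaction.** Section 5.2.7 names one chemotherapy interaction: "Anti-oxidants (e.g. vitamin C) may reduce the effect of some chemotherapeutic agents".
- **Unblinding.** Section 6.3.1: "The randomisation code for an individual participant may only be unblinded in emergency situations". Its specific examples are symptoms of vitamin C toxicity.

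**The concern.** The decision in section 5.2.8 is about the trial treatment, which is a blinded capsule with two possible contents. The question put to the oncologist is about vitamin C only. The researcher does not know which capsule the participant has, and the placebo is not described as inert.

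A researcher who asks only about 500mg vitamin C has therefore complied fully, even when the participant is swallowing a bacterial product that the oncologist was never told about. The protocol leaves it to the oncologist to decide what suits the chemotherapy regime. That decision should cover what the participant may actually be taking.

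What is at stake is the soundness of a safety clearance. The feasibility outcomes and the CRPS comparison are not touched.

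**Working it through.** The protocol gives no figure to reproduce. The check has two parts: a reading of the text, and a rough count of how many participants could be affected.

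**1. Does any other provision require the placebo contents to be reviewed?**

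| Place in Protocol | What it covers | Does it close the gap? |
|---|---|---|
| 2.3.1 and 2.3.3 (risks) | Vitamin C only | No |
| 4.4.2 (exclusions) | Vegans excluded because the placebo is dairy based | No. It is the only rule based on the placebo's contents, and it says nothing on chemotherapy |
| 5.2.7 (interactions) | Vitamin C only | No |
| 5.2.9 (stopping treatment) | "Requires early discontinuation for any other reason" | No. It permits a stop but requires no question about the placebo |
| 6.3.1 (breaking the blind) | Emergencies | No. Starting chemotherapy is not named |
| 5.2.1, Discontinuation of treatment (the section following 7.5.4) | "opening of randomization envelope so treating clinicians are aware of the dosage" | No. It applies once the capsule is stopped, so it does not reach someone cleared to continue |
| 6.3, Capturing and eliciting adverse event information | Asks at visits about new or changed medication | No. It may detect the chemotherapy but does not alter the question asked |

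There are two possible capsules, and review of one is required.

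**2. How many participants could be affected?**

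Inputs:

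- Arm size: "at least 50 participants per arm" (section 11.1), with block randomisation for balance (section 6). At the minimum this is 50 on placebo and 2 × 50 = 100 in all.
- Probability p of starting chemotherapy within the 50 days: not in the protocol, which only calls it rare. Assumed range: 0.001 to 0.005.

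The assumed range on a yearly scale, p × 365/50:

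- 0.001 × 7.3 = 0.0073, about 0.7% a year
- 0.005 × 7.3 = 0.0365, about 3.7% a year

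Expected chemotherapy starters:

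| | p = 0.001 | p = 0.005 |
|---|---|---|
| All participants, 100 × p | 0.1 | 0.5 |
| Placebo arm, 50 × p | 0.05 | 0.25 |
| Chance of none in the placebo arm, (1 − p)^50 | 0.999^50 = 0.95 | 0.995^50 = 0.78 |

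Given the assumed p, the placebo row is an upper bound on the number cleared without review of their product. Clearance also needs the participant to report the chemotherapy and the oncologist to accept vitamin C. The row counts people, not harm.

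**The case against.** The strongest reply is that section 5.2.8 does what it sets out to do. The protocol names one chemotherapy interaction, with antioxidants such as vitamin C. The procedure treats every participant as possibly on vitamin C, which is the cautious course under blinding. No hazard of the placebo during chemotherapy is documented, so an added question looks like preference rather than correction. Liaising with the oncologist does not forbid saying more, the investigator may stop treatment for any reason, and the unblinding rule leaves the investigator some judgement. The participant information form, not available here, may describe the placebo. The event is rare and the assumed rate has no source.

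Much of this stands. The one named interaction is covered for everyone, no hazard is shown, and the number affected is most likely zero. These points limit the importance.

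They do not repair the rule. Discretion to say more, or to stop, is not a duty to tell the oncologist what the capsule may contain. A procedure that assigns suitability to the oncologist should give that person the facts for both arms. The same objection brings out a further omission: the question does not mention the citrus bioflavonoids in the active capsule either.

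**Conclusion.** The point holds as a minor one. As written, a placebo participant who starts chemotherapy can be cleared to go on taking a capsule whose contents the oncologist was not asked about, and no other section prevents it.

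About half of participants take that capsule, but the procedure reaches only those who start chemotherapy within 50 days. That is an expected 0.05 to 0.25 people on placebo, resting entirely on the assumed 0.1% to 0.5% and on 50 per arm.

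Confidence is high about what the text requires. Nothing is claimed about harm, which the protocol gives no means of judging. The change is worth considering because it is cheap.

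**What to change.** Reword the sentence in section 5.2.8 along these lines:

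> The researcher will give the treating oncologist the contents of both possible capsules (section 5.2.1). The trial treatment continues only if both are acceptable for the chemotherapy regime, and is otherwise stopped immediately.

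Referring to the product tables brings in the citrus bioflavonoids as well. The clinical decision stays with the oncologist, and the clearance itself needs no unblinding.

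The cost is one sentence, with no new visit, staff or data. The downside is that a capsule may occasionally be stopped because of the product the participant is not taking. Under the discontinuation section following 7.5.4, such a stop also opens the envelope, although the stopping procedure in 5.2.9 does not call for that. With 0.1 to 0.5 chemotherapy starters expected in the whole trial under the same assumption, this would fall on well under one participant.
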